7.9.2.6 Immediately Reportable Event

Immediately reportable events (IREs) are events that must be reported immediately to MacroGenics Product Safety within 24 hours of being identified. IREs include but are not limited to:

- SAEs
- AEs leading to permanent discontinuation of study drug in an individual patient.
- All pregnancies and exposure during breastfeeding, from the time of treatment through 7 months following cessation of study treatment. All pregnant and/or lactating female partners of a male patient must be requested to complete a Pregnant Partner Consent Form so that pregnant partner, fetal, and/or newborn information can be collected. Upon confirmation of serum pregnancy testing, the patient will be followed for the outcome of pregnancy. All live newborns will be followed six months after the birth, and all necessary information will be collected to assess the effects of study drug on the newborn. If necessary, the follow-up period will be extended for the newborn.

- Adverse events of special interest (AESI) considered immediately reportable events as described in **Section 7.9.3** and below:
 - \geq Grade 3 Infusion-related reactions or CRS (see also **Section 6.5.1**)
 - irAE (see also **Section 6.5.2**)
 - Cardiotoxicity (see also **Section 6.5.3**)
- Administration of a dose significantly greater (+ 20%) than the planned dose of either margetuximab or pembrolizumab resulting in an event of clinical consequence.
- Any suspected transmission of an infectious agent via study drug (margetuximab or pembrolizumab).
- Withdrawal of the patient from study drug administration for any reason other than disease progression.
- Abnormal liver enzymes that meet the criteria for potential Hy's law, which is defined as AST and/or ALT that is greater than $3 \times$ ULN and total bilirubin that is greater than $2 \times$ ULN without any alternate etiology.

In those cases, in which the IRE is considered related to study drug and the event is of sufficient clinical concern to warrant study drug discontinuation, the study drug may be discontinued and the patient will continue participation in the study for observational safety and analysis (except for cases where the patient withdraws consent or is withdrawn from the study by the investigator). At any time after completion of the study, if an investigator becomes aware of a SAE that is suspected related to study drug, the investigator should report the event to MacroGenics Product Safety immediately.

A physician's assessment of the event is expected to be completed in conjunction with reporting an IRE to MacroGenics Product Safety.

7.9.3 Adverse Events of Special Interest

AESI will include the following:

- All Infusion reactions including cytokine release syndrome. (Grade 3 or greater will be reported as IREs)
- Immune-related AEs of Grade 3 or greater suggestive of an autoimmune process, including but not limited to: pneumonitis, colitis, autoimmune hepatitis, arthritis, glomerulonephritis, myocarditis and cardiomyopathy, hypophysitis, thyroiditis, myositis, uveitis, neurotoxicity, or other autoimmune endocrinopathies, pericarditis, or myocarditis
- Left ventricular dysfunction requiring delay or cessation of margetuximab
- Administration of an overdose, as defined in **Section 7.9.5.2** of either margetuximab or pembrolizumab resulting in an event of clinical consequence.

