6.5.2 Immune-Related Adverse Events

A high level of awareness for the possibility that an AE may be an immune-related AE (irAE) is necessary in the management of patients receiving pembrolizumab because the presentations of an irAE can be subtle, and other causes must be ruled out. An irAE can occur at any point during treatment with pembrolizumab. It is imperative to establish the correct diagnosis promptly, determining severity based on Common Terminology Criteria for Adverse Events (CTCAE) grading and initiating treatment with steroids, if necessary, and holding further pembrolizumab treatment is essential (49).

Immune checkpoint blockade therapies have been associated with several syndromes resulting from the breaking of immunological tolerance in normal tissues (34, 60, 72). These syndromes include but are not limited to: pneumonitis, colitis, autoimmune hepatitis, arthritis, glomerulonephritis, myocarditis and cardiomyopathy, hypophysitis, thyroiditis, or other autoimmune endocrinopathies. The occurrence of any of these syndromes dictates interruption and potentially discontinuation of study drug administration pending further evaluation and reporting them to the Sponsor as AESIs. Most low-grade immune-related AEs (irAEs) can be

managed symptomatically. Persistent low grade or moderate toxicities may require treatment with corticosteroids or in refractory cases other immune suppressing agents such as mycophenolate or infliximab. High-grade immune-related toxicities will, in almost all cases, require treatment with corticosteroids.

For the purposes of the safety management, no distinction should be made as to which drug is the causative agent and both agents stopped (temporarily held or discontinued).

Temporary interruptions of margetuximab and/or pembrolizumab may be required in the event of treatment-related immune-related toxicity. General guidelines for specific toxicity regarding dosing and treatment are provided below. All toxicities will be graded according to NCI CTCAE v4.03.

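### Protocol 6.5.2 and 7.9.3 set different grade limits for immune-related AESIs, 7.9.2.6 leaves the IRE limit unclear, and the SAP does not say which definition its AESI and IRE tables use

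*Protocol*

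**What the plan says.** Three protocol sections bear on when an immune-related AE is an AESI or an IRE.

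- **Protocol 7.9.3**, the AESI list, admits "Immune-related AEs of Grade 3 or greater suggestive of an autoimmune process". It names pneumonitis, colitis, autoimmune hepatitis, hypophysitis, thyroiditis, myocarditis and others.
- **Protocol 6.5.2**, on managing immune-related AEs, names largely the same syndromes. It then says: "The occurrence of any of these syndromes dictates interruption", and potentially discontinuation, "pending further evaluation and reporting them to the Sponsor as AESIs". The sentence carries no grade. The next one begins "Most low-grade immune-related AEs (irAEs) can be" and deals with low-grade events, so these are within the section's scope.
- **Protocol 7.9.2.6**, the list of events due to the sponsor within 24 hours, includes AESIs "considered immediately reportable events as described in Section 7.9.3 and below". Beneath that lead-in, infusion reactions carry a Grade 3 limit. The immune-related line, "irAE (see also Section 6.5.2"), carries none and points to 6.5.2.

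On the analysis side, Protocol 9.4.1 and SAP 6.7.1 each list AESIs and IREs among the summaries giving the number and percent of patients affected. The SAP expands the two abbreviations but gives no definition or grade rule for either. SAP 7 leaves table shells and programming specifications to a separate programming plan.

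**The concern.** Safety and tolerability of the combination are part of the first primary objective, and immune toxicity is a main expected risk of adding a checkpoint inhibitor. A reader of the study report will take the AESI table as the summary of that risk. If the protocol gives two grade limits for the same syndromes and the SAP chooses neither, the percentage in that table depends on a decision that is not written down.

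The same text sets a 24-hour reporting duty at about 29 institutions. Two sites could each follow the protocol in good faith and handle the same low-grade event differently.

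**Working it through.** No sample size, power or event figure bears on this point, so the check sets the passages side by side.

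**1. A test case.** Take a first, non-serious Grade 2 pneumonitis that does not lead to permanent discontinuation, and compare it with a Grade 3 pneumonitis.

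| Rule applied | Grade 2 | Grade 3 |
|---|---|---|
| Protocol 6.5.2 | AESI | AESI |
| Protocol 7.9.3 | not an AESI | AESI |
| Protocol 7.9.2.6, following its pointer to 6.5.2 | IRE | IRE |
| Protocol 7.9.2.6, following its lead-in to 7.9.3 | not an IRE | IRE |

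The first two rows contradict each other for Grade 2. The last two are alternative readings of one ambiguous line.

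**2. Is the difference deliberate?** Infusion reactions show how the protocol separates the two tiers when it means to. They are AESIs at every grade and IREs from Grade 3, and 7.9.2.6 and 7.9.3 agree on this. Immune-related AEs have no such consistent statement. Apart from infusion reactions, 7.9.3 does not itself say which AESIs are IREs.

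**3. A second instance.** Protocol 7.9.2.6 lists cardiotoxicity as an IRE without a grade and refers to 6.5.3, where 6.5.3.2 covers Grade 1 or 2 myocarditis. In 7.9.3 myocarditis appears only in the item limited to Grade 3 or greater. The IREs in that list are introduced as a subset of AESIs, so a Grade 2 myocarditis could be read as an IRE without meeting the AESI item that names it.

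**4. Does anything settle it?** I found no rule of precedence between these sections. The general definition of an AESI in Protocol 7.9.2.3 has no grade limit. SAP 6.7.1 is silent.

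**5. Size.** Let p be the proportion of patients with any listed immune-related AE, and f the share of those patients who reach Grade 3. The immune-related AESI percentage is p under 6.5.2 and p × f under 7.9.3, a ratio of 1/f. The documents give neither p nor f for this combination. The direction is known, since f cannot exceed 1: for syndromes named in both sections, 6.5.2 gives the same percentage or a higher one. The amount is not known.

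**The case against.** The strongest reply is that 7.9.3 is the dedicated AESI list and should govern, while the 6.5.2 sentence is loose introductory text. That sentence also says occurrence requires interruption, yet 6.5.2.3 gives no hold for Grade 1 pneumonitis, and 6.5.2.7 manages isolated hypothyroidism without interruption. It therefore cannot be literal at every grade. This has force for Grade 1. It does not dispose of Grade 2: 6.5.2.3, 6.5.2.5 and 6.5.2.7 hold both drugs for Grade 2 pneumonitis, nephritis and hyperthyroidism. At that grade the interruption half of the sentence agrees with the detailed rules, and nothing marks the reporting half as unintended.

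A reader might infer that 7.9.2.6 makes immune-related AEs reportable at any grade. The text does not support this. The line is ungraded but sits under a lead-in that cites 7.9.3, where immune-related AESIs already start at Grade 3, so a limit need not be repeated. The entry is ambiguous.

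A reader might also infer that the planned tables will mix two definitions because they count whatever sites flagged. SAP 6.7.1 does not say this. It mentions no site flag, and the programming plan is not among the documents. What can be said is that the SAP leaves the definition open.

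Finally, no recorded safety data drop out. SAP 6.7.1 tabulates all recorded TEAEs by organ class and preferred term, with separate tables for relatedness, Grade 3 or higher, interruption and withdrawal. Low-grade immune-related AEs that are serious or lead to permanent discontinuation are IREs in any case. All of this stands, and it limits the consequence to two descriptive tables and to 24-hour reporting.

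**Conclusion.** The point holds as an internal inconsistency. Protocol 6.5.2 and 7.9.3 disagree on whether a low-grade immune-related AE is an AESI, 7.9.2.6 is ambiguous on whether it is an IRE, and the SAP plans both tables without stating a definition. The reported AESI and IRE percentages, and the 24-hour reporting that sites carry out, can therefore vary by site or by reading. Efficacy analyses and the DLT rules are unaffected.

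The size cannot be calculated. It is tempting to attach a figure: if a quarter of patients with an immune-related AE reach Grade 3, the two definitions differ by 1/0.25 = 4-fold. That only restates the assumed quarter, for which the documents give no basis, and it should not be cited as an estimate.

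The conclusion rests on a plain reading of 6.5.2 at Grade 2 and on the absence of a precedence rule. A definition in the unseen programming plan could settle the tables, but it would not remove the conflict in what sites are told to report. The change should be made because it is cheap and the tables describe a primary objective.

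**What to change.** 1. **Protocol.** Reconcile 6.5.2, 7.9.2.6 and 7.9.3, with the myocarditis entries in 6.5.3.2, to one AESI definition and one IRE definition. The sponsor settles the grade threshold for each; they may differ, as they do for infusion reactions.
2. **SAP 6.7.1.** State both definitions.
3. **SAP 6.7.1, AESI table.** Derive the immune-related AESI table from all recorded TEAEs with a prespecified MedDRA term list, showing all-grade and Grade 3 or higher columns. State whether the investigator's attribution is also required, since some terms, such as diarrhea, are not immune-related in every patient. The table then no longer depends on which protocol section a site followed.

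The cost is wording in the protocol and SAP, a term list and one extra column. Protocol 7.9.4 and 7.9.5 already require AEs to be graded and entered on the eCRF, so the AESI table should need no new data collection. The derivation cannot correct past differences in 24-hour reporting, so the report should say whether the IRE table shows events as reported or as derived.

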7.9.4 Performing Adverse Event Assessments

Medical evaluation and classification of the adverse event must be performed by the investigator who is qualified to review AE information. The determination of seriousness, severity and causality must be made according to the following criteria:

Assessment of Seriousness: Event *seriousness* will be determined according to the definition of an SAE in [Section 7.9.2](#). Seriousness serves as a guide for defining regulatory reporting obligations for AEs.

Assessment of Severity: Event *severity* will be assigned according to the investigator's assessment using the CTCAE Version 4.03 (for described events and syndromes). For events not contained in CTCAE, the investigator may assign severity according to the following scale:

- Grade 1 = Mild
- Grade 2 = Moderate AE
- Grade 3 = Severe AE
- Grade 4 = Life-threatening or disabling AE
- Grade 5 = Death related to AE

Any event or laboratory value judged as Grade 4 severity should be separately evaluated to determine whether it also meets the serious criterion of "immediately life threatening" (see [Section 7.9.2.5](#)).

Note: Severity is not synonymous with seriousness. The term "severe" is often used to describe the intensity (severity) of a specific event. The event itself, however, may be of relatively minor medical significance (such as severe headache). This is not the same as "serious," which is based on patient/event outcome or action criteria usually associated with events that pose a threat to a patient's life or functioning.

Assessment of Causality: The investigator is required to provide an assessment of causality or relationship of AEs to the study drug based on 1) temporal relationship of the event to the administration of study drug; 2) whether an alternative etiology has been identified, and 3) biological plausibility. Causality must be assessed separately for each drug. The causality assessment categories that will be used for this study are described below.

Causality assessments that are considered **not related** to study drug:

None: The event is related to an etiology other than the study drug (the alternative etiology should be documented in the patient's medical record).

Unlikely: The event is unlikely to be related to the study drug and likely to be related to factors other than study drug.

If an SAE is considered "unlikely" or "unrelated" to study drug, the investigator should offer his/her clinical opinion as to what factor(s), agent(s), or process(es) were the likely causative mechanism for the event.

Causality assessments that are considered **related** to study drug:

Possible: There is an association between the event and the administration of the study drug and there is a plausible mechanism for the event to be related to study drug; but there may also be alternative etiology, such as characteristics of the patient's clinical status or underlying disease.

Probable: There is an association between the event and the administration of study drug, a plausible mechanism for the event to be related to the study drug and the event could not be reasonably explained by known characteristics of the patient's clinical status or an alternative etiology is not apparent.

Definite: There is an association between the event and the administration of study drug; a plausible mechanism for the event to be related to the study drug and causes other than the study drug has been ruled out and/or the event re-appeared on re-exposure to the study drug.

Assessment of Expectedness: As part of the regulatory reporting requirements, the Sponsor must perform an assessment of expectedness (expected/unexpected from the perspective of previously observed, not on the basis of what might be anticipated from the pharmacological properties of a medicinal product) for AEs. Adverse reactions will be considered unexpected if the nature, seriousness, severity or outcome of the reaction(s) is not consistent with the reference information (e.g., the Adverse Drug Reaction section of the investigator's brochure [IB]) for the study product.

7.9.5 Reporting of Adverse Events to the Sponsor

Throughout the study, the investigator must document all AEs on the eCRF in a timely manner. Adverse events will be collected and followed from the time the patient provides informed consent for the study (see [Section 7.1](#)) until 28 days following the last dose of study drug or the End of Treatment Visit or until the start of a subsequent systemic anticancer therapy (whichever occurs first). After the completion of the 28 day-period or start of a subsequent systemic anticancer therapy, only treatment-related AEs will be reported. If a patient experiences an AE after the informed consent document is signed and prior to treatment with study drug, it should be captured as medical history; however, if the investigator believes the AE may have been caused by a protocol-related procedure it will be recorded as an AE and entered onto the eCRF.

To identify the occurrence of any new medical complaints or worsening of previous complaints, non-leading questioning should be posed to the patient.

Events related to disease progression/worsening of underlying disease (including those with a fatal outcome) will be collected as efficacy endpoints, and not documented as AEs/SAEs. These events may not qualify for expedited reporting to regulatory agencies if consistent with expected rates of progression for the underlying disease. However, if an AE/SAE occurs in a patient and it is unclear if the event is due to progressive disease, the AE/SAE should be reported.

Any serious adverse event, or follow up to a serious adverse event, including death due to any cause other than progression of the cancer that occurs to any patient from the time the consent is signed through 90 days following cessation of treatment, or 28 days following cessation of treatment if the patient initiates new anticancer therapy, whichever is earlier, whether or not related to the Sponsor's product, must be reported within 24 hours to the Sponsor.

After 28 days following the last dose of study drug administration, if an Investigator becomes aware of an SAE that s/he suspects is related to study drug, the Investigator should report the event to the Sponsor.

If a patient reports signs and symptoms that represent a single medical syndrome, diagnosis, or concept, the syndrome/diagnosis/concept should be documented (e.g., cough, runny nose, fever = Upper Respiratory Tract Infection) in the eCRF.

The investigator must follow all SAEs until resolution and record the date of resolution. Resolution of an event is defined as the return to pre-treatment status or stabilization of the condition with the expectation that it will remain chronic.

Adverse events occurring after the patient completes the trial or after early termination need not be reported unless the event is serious and the investigator believes that the event may have been caused by the study drug or a protocol procedure. All pending pregnancy outcomes will be reported to the Sponsor after completion of the trial. It is the responsibility of investigators or their designees to report any pregnancy or lactation in a patient (spontaneously reported to them) that occurs during the trial or within 7 months of completing the trial.

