7.9 Safety Assessments

7.9.1 Criteria for Evaluation

All AEs and SAEs, regardless of causality, will be reported from the time a signed and dated ICF (see [Section 7.1](#)) is obtained through 28 days following the last dose of study drug or the End of Treatment Visit or until the start of a subsequent systemic anticancer therapy (whichever occurs first). After the completion of the 28 day-period or start of a subsequent systemic anticancer therapy, only treatment-related AEs will be reported.

- Protocol-related AEs and SAEs will be collected from the time the patient has consented to study participation.
- AEs reported after the informed consent document is signed and prior to treatment with study drug should be captured as medical history; however, if the Investigator believes the AE may have been caused by a protocol procedure it will be reported to the Sponsor or its designee and/or entered on the eCRF. SAEs considered related to study drug should be reported at any time, even after the patient's final visit.
- Progression of the underlying neoplasm resulting in hospitalization or death (e.g., patient hospitalized for or dies from PD only, without any other SAE) will be documented as an antitumor activity outcome and not as an SAE, unless considered as drug-related by the investigator. If an SAE occurs in a patient and it is unclear whether the event is related to PD, the SAE should be reported.
- The reporting of laboratory/vital signs abnormalities as both laboratory findings and AEs should be avoided. They should not be reported as AEs unless any one of the following are met:
 - Any criterion for an SAE is fulfilled
 - The laboratory/vital signs abnormality causes the patient to discontinue from the study treatment
 - The laboratory/vital signs abnormality causes the patient to interrupt the study treatment

- The laboratory/vital signs abnormality requires intervention
- The laboratory/vital signs are deemed clinically significant, based on medical judgement.

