7.9.2 Adverse Event: Definitions

7.9.2.1 Adverse Event

Progression of the cancer under study is not considered an adverse event unless it is considered to be drug-related by the investigator.

An adverse event is any untoward medical occurrence in a patient or clinical investigation patient administered a pharmaceutical product and which does not necessarily have to have a causal relationship with this treatment. An AE can therefore be any unfavorable and unintended sign (e.g., an abnormal laboratory finding), symptom, or disease temporally associated with the use of a medicinal product, whether or not considered related to the medicinal product.

An adverse event will also be considered to be any untoward effect of a study-related procedure, which is conducted after signed informed consent and prior to study drug administration.

All adverse events will be recorded from the time the consent form is signed through 28 days following cessation of treatment and at each examination on the Adverse Event case report forms/worksheets. The reporting timeframe for adverse events meeting any serious criteria is described in [Section 7.9.6](#) - Notification to the Sponsor of Events Requiring Immediate Reporting.

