#### 5.1.2 Time to Event Endpoints

- Progression-free survival (PFS): The PFS is defined as the time from the first dose date to the date of first documented progression or death from any cause, whichever occurs first. For patients who are not known to be dead or progressed at the time of data cut-off for PFS analysis, the PFS will be censored at the date of the last tumor assessment. The documented progression is determined by radiographic assessment using RECIST v1.1. PFS will be calculated as:

$$\text{PFS (months)} = (\text{date of event [documented progression or death] or date of censoring} - \text{first dose date} + 1) / (365.25/12)$$

- Duration of response (DoR): The DoR is defined as the time from the date of initial response to the date of first documented progression or death from any cause, whichever occurs first. DoR will be analyzed for responding patients only. For responding patients who are not known to be dead or progressed at the time of data cut-off for DoR analysis, the DoR will be censored at the date of the last tumor assessment. The documented progression is determined by radiographic assessment using RECIST v1.1. DoR will be calculated as:

$$\text{DoR(months)} = (\text{date of event [documented progression or death] or date of censoring} - \text{date of initial response} + 1) / (365.25/12)$$

DoR may also be determined by irRECIST.

- Overall survival (OS): The OS is defined as the time from the first dose date to the date of death from any cause. For patients who are not known to be dead at the time of data cut-off for OS analysis, the OS will be censored at the time they are last known to be alive. OS will be calculated as:

$$\text{OS (months)} = (\text{date of death or last known alive} - \text{first dose date} + 1) / (365.25/12)$$

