## **5.2 Safety Endpoints**

### **5.2.1 Adverse Events**

Safety will primarily be addressed by evaluations of adverse events (AEs). An AE is defined as any untoward medical occurrence in a patient or clinical investigation subject, occurring as part of a research study, which does not necessarily have to have a causal relationship with use of a medicinal product. An AE can therefore be any unfavorable and unintended sign (including an abnormal laboratory finding, for example), symptom, or disease whether or not considered related to the medicinal product.

AEs will be captured starting with signing of the informed consent form through 28 days following cessation of treatment. Only treatment-related serious AEs will be captured afterwards. These events will be recorded by the Investigators in the eCRFs. Verbatim terms will be coded to lower-level terms using the most recent version of the Medical Dictionary for Regulatory Activities (MedDRA).

Only treatment-emergent adverse events (TEAEs) will be summarized as safety endpoints. A TEAE is defined as any event that is newly occurring on or after the administration of study drug or an event that existed before but increased in severity on or after study drug administration. For each TEAE, a new AE is recorded whenever the toxicity/severity changes. AEs that occurred before and did not worsen on or after study drug administration are considered non-treatment emergent AEs and will only be summarized as medical history.

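### Protocol 7.9.5 exempts more progression-related events from AE/SAE reporting than 7.9.1 and 7.9.2.1 do, so some non-fatal tumour complications may reach neither the safety tables nor any efficacy endpoint

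*Protocol*

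**What the plan says.** The protocol states the rule on progression and AE reporting in several places.

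- **Section 7.9.5**, on reporting to the sponsor, has the widest version: "Events related to disease progression/worsening of underlying disease (including those with a fatal outcome) will be collected as efficacy endpoints, and not documented" as AEs or SAEs. The same paragraph adds a safeguard: where "it is unclear if the event is due to progressive disease, the AE/SAE should be reported".
- **The next paragraph of 7.9.5**, on 24-hour SAE reporting, is narrower. It covers serious events "including death due to any cause other than progression of the cancer", regardless of relationship to the sponsor's product.
- **Section 7.9.1** covers progression that leads to hospitalization or death from PD alone, with no other SAE. Such a case "will be documented as an antitumor activity outcome and not as an SAE, unless considered as drug-related by the investigator".
- **Section 7.9.2.1** says: "Progression of the cancer under study is not considered an adverse event unless it is considered to be drug-related by the investigator".
- **The synopsis** (Safety Assessments) repeats the 7.9.1 scope without the drug-related exception.

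On the analysis side, SAP 5.1.1, 5.1.2 and 6.6.3 list response, PFS, DoR, OS and tumour size. For PFS and DoR, "The documented progression is determined by radiographic assessment using RECIST v1.1". SAP 6.7.1 builds the safety tables from TEAEs recorded in the eCRF.

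**The concern.** An event related to progression is a larger class than progression itself. It can include bleeding, obstruction or perforation at a tumour site. If a site follows 7.9.5, such an event is left out of the AE record once the investigator attributes it to the disease. If the site follows 7.9.1 and 7.9.2.1, it is recorded and its causality is assessed.

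Safety is a primary objective, and the trial is open-label with no control arm. The all-cause summaries (any TEAE, Grade 3 or higher, SAE, fatal AE) should not depend on an investigator's view of cause or on which section a site reads. The setting makes such attributions likely to arise: Section 4.1.1 lets clinically stable patients continue both drugs after first meeting conventional progression criteria.

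**Working it through.** No calculation tests this point, and the plan gives no figure to reproduce. The check is a comparison of the rules, followed by four types of event.

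| Place | What is exempt | Kept if drug-related? | Unclear cases |
|---|---|---|---|
| Synopsis | Hospitalization or death from PD alone | Not stated | SAE reported |
| 7.9.1 | Hospitalization or death from PD alone | Yes | SAE reported |
| 7.9.2.1 | Progression of the cancer | Yes | Not stated |
| 7.9.5, progression paragraph | Any event related to progression or worsening, fatal included | Not stated | AE/SAE reported |
| 7.9.5, SAE paragraph | Death from progression | Not stated for such deaths | Not stated |

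The fourth row differs from the others in scope. Rows one, four and five lack the exception given in rows two and three.

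**Type 1: non-fatal complication, clearly attributed to the tumour, no RECIST progression on the scan.** Under 7.9.1 and 7.9.2.1 it is not progression itself, so it is an AE. Under the 7.9.5 sentence it is not. That sentence sends it to the efficacy endpoints, but none receives it: response, PFS and DoR use radiographic progression (PFS and DoR also count death), OS counts death, and SAP 6.6.3 uses target-lesion sums. Appendix 7 says symptomatic deterioration does not describe an objective response. If RECIST progression has already been recorded and treatment continues, PFS has already had its event and a later complication adds nothing to it. Since SAP 6.7.1 uses only recorded TEAEs, the event appears in no planned safety or efficacy summary.

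**Type 2: fatal complication, clearly attributed to the tumour.** OS counts the death. PFS and DoR count it unless SAP Table 2 censors it, for example after two or more consecutive missed assessments. It can still be absent from the SAE and fatal-AE tables if the site follows the first 7.9.5 sentence.

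**Type 3: progression the investigator considers drug-related.** It is kept by 7.9.1 and 7.9.2.1. The 7.9.5 sentence and the synopsis are silent, but 7.9.1 separately requires SAEs related to study drug to be reported at any time.

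**Type 4: cause unclear.** 7.9.5 requires reporting, and 7.9.1 and the synopsis do so for SAEs. There is no gap.

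Type 1 is therefore the firm case. Type 2 is a gap in the safety tables only.

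The direction is fixed, because leaving events out can only lower a count. For scale only: one patient omitted from a category lowers its percentage by 1/85 = 1.2 points in the full expansion phase, or 1/30 = 3.3 points in one Part B region, and only if the patient had no other event in that category. This converts units; it does not estimate how many patients are affected.

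**The case against.** The strongest reply is that the protocol already limits the damage. The rule for unclear cases stands in the same paragraph as the wide sentence, so only events confidently attributed to progression drop out. An investigator who suspects the drug will seldom call an event clearly due to the cancer, and related SAEs have their own route in 7.9.1. Section 7.9.5.1 says Grade 3 and 4 laboratory findings should be reported as AEs or SAEs, so severe anaemia from a bleed could still be recorded. All of this stands and narrows the point. None of it covers a non-fatal clinical event that the investigator is sure comes from the tumour.

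A reader might infer three stronger things that the documents do not support.

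- *That every progression-related event, deaths included, escapes all endpoints.* OS counts every death, and unclear cases are reported.
- *That the safety tables are shown to be understated by some amount.* There is no event rate, and the loss depends on which section sites follow.
- *That 7.9.5 also contradicts the AE definition, which covers a* "symptom, or disease whether or not considered related to the medicinal product". That phrase concerns relationship to the drug, and 7.9.2.1 itself places a progression exemption before its own definition.

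**Conclusion.** The inconsistency is real and should be corrected. Section 7.9.5 is wider than 7.9.1, 7.9.2.1 and its own following paragraph, and its sentence omits the drug-related exception; the synopsis omits the exception too. The consequence is inconsistent capture between sites, with any error toward lower all-cause TEAE, Grade 3 or higher, SAE and fatal-AE counts.

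The conclusion rests on two conditions: that some sites apply the 7.9.5 sentence as written, and that some on-study complications are clearly attributed to the tumour. The documents support neither a number of affected patients nor a claim that fatal events are lost to efficacy analysis.

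**What to change.** Replace the 7.9.5 sentence with the rule already in 7.9.1 and 7.9.2.1. Only progression of the cancer itself is exempt, including hospitalization or death from PD alone with no other SAE, and it is reported if the investigator considers it drug-related. State that all other clinical events are recorded as AEs or SAEs with causality assessed. Keep the hospitalization exemption, since dropping it would create a new rule. Keep the rule for unclear cases. Add the drug-related exception to the synopsis so that it, 7.9.1, 7.9.2.1 and 7.9.5 agree.

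A summary of deaths by cause alongside the SAP 6.7.1 tables would help, but it is optional. The table shells are in a separate programming plan, so its absence there cannot be assumed.

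The cost is wording in two places, a few more AE and SAE records, and slightly higher reported rates. Section 2.3.1.1 reports 64 patients already treated in this study by 30 September 2017. New wording does not by itself recover events left unrecorded for them, so capture may differ before and after the change, and the study report should say so.
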